#### 7.1.4.2 Blinding/Unblinding

N/A

#### 7.1.5 Visit Requirements

Visit requirements are outlined in Section 6.0 - Trial Flow Chart. Specific procedure-related details are provided above in Section 7.1 - Trial Procedures.

##### 7.1.5.1 Screening

###### 7.1.5.1.1 Screening Period (day -14 to day -1)

Unless otherwise noted, evaluations may be performed up to 2 weeks prior to Cycle 1 Day 1 of treatment. Informed consent should be obtained prior to any screening procedure.

Clinical evaluation: demographics and medical history, prior and concomitant medications, full physical examination to include height (baseline only) and weight, ECOG performance status.

###### Laboratory studies:

- **Pregnancy Test:** A serum or urine pregnancy test ( $\beta$ -HCG) is required for all women of childbearing potential at screening within 72 hours prior to the first dose of azacitidine. If urine test is positive or cannot be confirmed as negative, a serum pregnancy test will be required.
- **CBC with differential and platelets**
- **Serum Chemistries (include Comprehensive Chemistry, uric acid, phosphate, magnesium):** These include the following parameters: sodium, potassium, chloride, bicarbonate (or CO2), LDH, BUN, serum creatinine, glucose, calcium, magnesium, phosphorus, uric acid, total protein, and albumin
- **LFTs:** These include total bilirubin (direct if total bilirubin is elevated), alkaline phosphatase, AST (SGOT), ALT (SGPT)
- **Thyroid Function Tests:** These include TSH and if clinically appropriate free T3 and T4
- **Coagulation Tests:** These include PT/INR, aPTT, and fibrinogen
- **Urinalysis**
- **Electrocardiogram**
- **Echocardiogram**
  - If an echocardiogram was conducted within the 3 months prior to the screening date and the patient has not received any chemotherapy in the time between and has not experienced any cardiac symptoms or events (heart attack, chest pain, arrhythmia etc), then the screening

echocardiogram does not need to be repeated, unless it is clinically indicated per investigator's discretion.

**Tissue Acquisition/Disease Assessment:** Primary tumor will be collected by peripheral blood and bone marrow biopsy. Bone marrow biopsy and blood sample should be obtained within 14 days prior to day 1 of treatment.

#### **7.1.5.2 Treatment Period**

Subjects will be followed with provider visits, physical exams, adverse event monitoring, laboratory tests, disease assessments as per the Trial Flow Chart 6.0. Collection of specimens for exploratory correlative studies will be done according to Trial Flow Chart 6.0

#### **7.1.5.3 Post-Treatment Visits**

##### **7.1.5.3.1 Safety Follow-Up Visit**

The mandatory Safety Follow-Up Visit should be conducted approximately 30 days after the last dose of trial treatment or before the initiation of a new anti-cancer treatment, whichever comes first. All AEs that occur prior to the Safety Follow-Up Visit should be recorded. Subjects with an AE of Grade > 1 will be followed until the resolution of the AE to Grade 0-1 or until the beginning of a new anti-neoplastic therapy, whichever occurs first. SAEs that occur within 90 days of the end of treatment or before initiation of a new anti-cancer treatment should also be followed and recorded. Subjects who are eligible for retreatment with azacitidine/pembrolizumab (as described in Section 7.1.5.5) may have up to two safety follow-up visits, one after the Treatment Period and one after the Second Course Phase.

##### **7.1.5.4 Follow-up Visits**

Subjects who discontinue trial treatment for a reason other than disease progression will move into the Follow-Up Phase and should be assessed every 8 weeks ( $\pm$  14 days) as per Trial Flow Chart including by bone marrow exam every 4-6 months to monitor disease status as appropriate. Every effort should be made to collect information regarding disease status until the start of new anti-neoplastic therapy, disease progression, death, end of the study or if the subject begins retreatment with azacitidine/pembrolizumab as detailed in Section 7.1.5.5. Information regarding post-study anti-neoplastic treatment will be collected if new treatment is initiated.

Subjects who are eligible to receive retreatment with azacitidine/pembrolizumab according to the criteria in Section 7.1.5.5 will move from the follow-up phase to the Second Course Phase when they experience disease progression/relapse. Details are provided in Section 5.9.1. The same procedures will need to be followed for Retreatment as per Trial Flow Chart for Initial Treatment.

#### **7.1.5.4.1 Survival Follow-up**

Once a subject experiences confirmed disease progression or starts a new anti-cancer therapy, the subject moves into the survival follow-up phase and should be contacted by telephone every 12 weeks to assess for survival status until death, withdrawal of consent, or the end of the study, whichever occurs first.

#### **7.1.5.5 Second Course Phase (Retreatment Period)**

Subjects who stop azacitidine/pembrolizumab with CR/CRI may be eligible for up to one year of additional azacitidine/pembrolizumab therapy if they progress after stopping study treatment. This retreatment is termed the Second Course Phase of this study and is only available if the study remains open and the subject meets the following conditions:

- **Either**

- Stopped initial treatment with azacitidine/pembrolizumab after attaining an investigator-determined confirmed CR/CRI
  - Was treated for at least 6 cycles with azacitidine/pembrolizumab before discontinuing therapy
  - Received at least four treatments with azacitidine/pembrolizumab beyond the date when the initial CR/CRI was declared

**OR**

- Had SD, MLFS, PR or CR and stopped pembrolizumab treatment after 24 months of study therapy for reasons other than disease progression or intolerance

**AND**

- Experienced an investigator-determined bone marrow confirmed disease progression after stopping their initial treatment with azacitidine/pembrolizumab
- Did not receive any anti-cancer treatment since the last dose of azacitidine/pembrolizumab
- Has a performance status of 0 or 1 on the ECOG Performance Scale
- Demonstrates adequate counts and organ function as detailed in Section 5.1.2/5.1.3
- Female subject of childbearing potential should have a negative serum or urine pregnancy test within 72 hours prior to receiving retreatment with study medication.

- Female subject of childbearing potential should be willing to use 2 methods of birth control or be surgically sterile, or abstain from heterosexual activity for the course of the study through 120 days after the last dose of study medication (Reference Section 5.8.2). Subjects of child bearing potential are those who have not been surgically sterilized or have been free from menses for > 1 year.
- Male subject should agree to use an adequate method of contraception starting with the first dose of study therapy through 120 days after the last dose of study therapy.
- Does not have a history or current evidence of any condition, therapy, or laboratory abnormality that might interfere with the subject's participation for the full duration of the trial or is not in the best interest of the subject to participate, in the opinion of the treating investigator.

Subjects who restart treatment will be retreated at the same dose and dose interval as when they last received pembrolizumab. Treatment will be administered for up to one additional year.

Visit requirements are outlined in Section 6.0 – Trial Flow Chart and should follow the same procedure as for initial treatment.

## 7.2 Assessing and Recording Adverse Events

An adverse event is defined as any untoward medical occurrence in a patient or clinical investigation subject administered a pharmaceutical product and which does not necessarily have to have a causal relationship with this treatment. An adverse event can therefore be any unfavorable and unintended sign (including an abnormal laboratory finding, for example), symptom, or disease temporally associated with the use of a medicinal product or protocol-specified procedure, whether or not considered related to the medicinal product or protocol-specified procedure. Any worsening (i.e., any clinically significant adverse change in frequency and/or intensity) of a preexisting condition that is temporally associated with the use of the investigational products, is also an adverse event.

Changes resulting from normal growth and development that do not vary significantly in frequency or severity from expected levels are not to be considered adverse events. Examples of this may include, but are not limited to, teething, typical crying in infants and children and onset of menses or menopause occurring at a physiologically appropriate time.

Merck product includes any pharmaceutical product, biological product, device, diagnostic agent or protocol-specified procedure, whether investigational (including placebo or active comparator medication) or marketed, manufactured by, licensed by, provided by or distributed by Merck for human use.

Adverse events may occur during the course of the use of Merck product in clinical trials or as prescribed in clinical practice, from overdose (whether accidental or intentional), from abuse and from withdrawal.

Progression of the cancer under study is not considered an adverse event.

All adverse events that occur after the consent form is signed but before treatment allocation/randomization must be reported by the investigator if they cause the subject to be excluded from the trial, or are the result of a protocol-specified intervention, including but not limited to washout or discontinuation of usual therapy, diet, placebo treatment or a procedure.

From the time of treatment allocation/randomization through 30 days following cessation of treatment, all adverse events must be reported by the investigator. Such events will be recorded at each examination on the Adverse Event case report forms/worksheets. The reporting timeframe for adverse events meeting any serious criteria is described in section 7.2.3.1. The investigator will make every attempt to follow all subjects with non-serious adverse events for outcome.

Adverse events will not be collected for subjects during the pre-screening period as long as that subject has not undergone any protocol-specified procedure or intervention. If the subject requires a blood draw, fresh tumor biopsy etc., the subject is first required to provide consent to the main study and AEs will be captured according to guidelines for standard AE reporting.

All adverse events will be recorded from the time the consent form is signed through 30 days following cessation of treatment and at each examination on the Adverse Event case report forms/worksheets. The reporting timeframe for adverse events meeting any serious criteria is described in section 7.2.3.

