Bone marrow biopsy/aspirate will be performed after 2 and 6 cycles of therapy, and every 3-6 months thereafter as described in Section 6.0 Trial Flow Chart. Treatment with azacitidine/pembrolizumab will continue until confirmed disease progression, unacceptable toxicity, or if patient is withdrawn from study for other reasons (Section 5.9). Patients having a clinical benefit from this treatment combination including CR/CRI but also those who achieve response less than CR/CRI (ie., PR/MLFS/HI/SD) will be able to continue on treatment on clinical study (AZA and pembrolizumab) until they meet criteria specified in section 5.9. After the end of treatment, each subject will be followed for 30 days for AEs monitoring (serious adverse events will be collected for 90 days after the end of treatment as described in Section 7.2.3.3.2.). Subjects who discontinue treatment for reasons other than disease progression will have post-treatment follow up for disease status until disease progression, initiating non-study cancer treatment, withdrawing consent or becoming lost for follow up. All subjects will be followed for overall survival until death, withdrawal of consent or the end of the study, whichever comes first.

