#### 5.2.1.4 Immune Adverse Events Associated with Pembrolizumab

Adverse events (both non-serious and serious) associated with pembrolizumab exposure may represent an immunologic etiology. These adverse events may occur shortly after the first dose or several months after the last dose of treatment. Pembrolizumab must be withheld for drug-related toxicities and severe or life-threatening AEs as per Table 4 below. See Section 5.7.5 for supportive care guidelines, including use of corticosteroids.

Table 4. Dose Modification and Toxicity Management Guidelines for Immune-related AEs Associated with Pembrolizumab

General instructions:
1. Corticosteroid taper should be initiated upon AE improving to Grade 1 or less and continue to taper over at least 4 weeks.

2. For situations where pembrolizumab has been withheld, pembrolizumab can be resumed after AE has been reduced to Grade 1 or 0 and corticosteroid has been tapered. For Grade 3 (excluding alopecia, fatigue) toxicities which are eligible for re-dosing: Increase dose interval to every 4 weeks, and to every 6 weeks with second occurrence. Pembrolizumab should be permanently discontinued if AE does not resolve within 12 weeks of last dose or corticosteroids cannot be reduced to  $\leq 10$  mg prednisone or equivalent per day within 12 weeks.
3. For severe and life-threatening irAEs, IV corticosteroid should be initiated first followed by oral steroid. Other immunosuppressive treatment should be initiated if irAEs cannot be controlled by corticosteroids.

Immune-related AEs	Toxicity grade or conditions (CTCAEv4.0)	Action taken to pembrolizumab	irAE management with corticosteroid and/or other therapies	Monitor and follow-up
Pneumonitis	Grade 2	Withhold	
 
• Administer corticosteroids (initial dose of 1-2 mg/kg prednisone or equivalent) followed by taper
 
	
 
• Monitor participants for signs and symptoms of pneumonitis
 
• Evaluate participants with suspected pneumonitis with radiographic imaging and initiate corticosteroid treatment
 
• Add prophylactic antibiotics for opportunistic infections
 

	Grade 3 or 4, or recurrent Grade 2	Permanently discontinue		

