The End of Treatment and Follow-up visit procedures are listed in Section 6 (Protocol Flow Chart) and Section 7.1.5 (Visit Requirements). After the end of treatment, each subject will be followed for 30 days for adverse event monitoring (serious adverse events will be collected for 90 days after the end of treatment as described in Section 7.2.3.3.2). Subjects who discontinue for reasons other than progressive disease will have post-treatment follow-up for disease status until disease progression, initiating a non-study cancer treatment, withdrawing consent or becoming lost to follow-up. After documented disease progression each subject will be followed by telephone for overall survival until death, withdrawal of consent, or the end of the study, whichever occurs first.

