#### **7.2.3.3.2 Reporting Adverse Events to the Coordinating Center (Sponsor) and to Merck Global Safety**

Participating sites will report to the Coordinating Center (Sponsor) all events meeting the criteria of serious adverse events utilizing the MedWatch 3500A form within 24 hours of the site becoming aware of the event and to Merck Global Safety within 2 working days. The Coordinating Center, JHU, as the sponsor of the study, will make the final determination regarding FDA submission. Thus, the Coordinating Center will be responsible for reporting to the FDA.

For the time period beginning when the consent form is signed until treatment allocation/randomization, any serious adverse event, or follow up to a serious adverse event, including death due to any cause other than progression of the cancer under study (Section 7.2.3.5) that occurs to any subject must be reported within 24 hours to the Coordinating Center (Sponsor) and within 2 working days to Merck Global Safety if it causes the subject to be excluded from the trial, or is the result of a protocol-specified intervention, including but not limited to washout or discontinuation of usual therapy, diet, placebo treatment or a procedure.

For the time period beginning at treatment allocation/randomization through 90 days following cessation of treatment, or 30 days following cessation of treatment if the subject initiates new anticancer therapy, whichever is earlier, any serious adverse event, or follow up to a serious adverse event, including death due to any cause other than progression of the cancer under study (Section 7.2.3.5) whether or not related to the Merck product, must be reported within 24 hours to the Coordinating Center (Sponsor) and within 2 working days to Merck Global Safety.

Additionally, any serious adverse event, considered by an investigator who is a qualified physician to be related to Merck product that is brought to the attention of the investigator at any time following consent through the end of the specified safety follow-up period specified in the paragraph above, or at any time outside of the time period specified in the previous paragraph also must be reported immediately to the Coordinating Center and to Merck Global Safety.

All subjects with serious adverse events must be followed up for outcome.

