#### **7.2.3.4 Events of Clinical Interest**

Selected non-serious and serious adverse events are also known as Events of Clinical Interest (ECI) and must be reported within 24 hours to the Sponsor and within 2 working days to Merck Global Safety. (Attn: Worldwide Product Safety; [contact])

For the time period beginning when the consent form is signed until treatment allocation/randomization, any ECI, or follow up to an ECI, that occurs to any subject must be reported within 24 hours to the Sponsor and within 2 working days to Merck Global Safety if it causes the subject to be excluded from the trial, or is the result of a protocol-specified intervention, including but not limited to washout or discontinuation of usual therapy, diet, placebo treatment or a procedure.

For the time period beginning at treatment allocation/randomization through 90 days following cessation of treatment, or 30 days following cessation of treatment if the subject initiates new anticancer therapy, whichever is earlier, any ECI, or follow up to an ECI, whether or not related to Merck product, must be reported within 24 hours to the Sponsor and within 24 hours to Merck Global Safety.

Events of clinical interest for this trial include:

1. an overdose of Merck product, as defined in Section 7.2.1 - Definition of an Overdose for This Protocol and Reporting of Overdose to the Sponsor, that is not associated with clinical symptoms or abnormal laboratory results.
2. an elevated AST or ALT lab value that is greater than or equal to 3X the upper limit of normal and an elevated total bilirubin lab value that is greater than or equal to 2X the upper limit of normal and, at the same time, an alkaline phosphatase lab value that is less than 2X the upper limit of normal, as determined by way of protocol-specified laboratory testing or unscheduled laboratory testing.\*

\*Note: These criteria are based upon available regulatory guidance documents. The purpose of the criteria is to specify a threshold of abnormal hepatic tests that may require an additional evaluation for an underlying etiology. The trial site guidance for assessment and follow up of these criteria can be found in the Investigator Trial File Binder (or equivalent).

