	Is a new cancer; (that is not a condition of the study) (although not serious per ICH definition, is reportable to the Sponsor within 24 hours and to Merck within 2 working days to meet certain local requirements); or	
Duration	Is an overdose (whether accidental or intentional). Any adverse event associated with an overdose is considered a serious adverse event for collection purposes. An overdose that is not associated with an adverse event is considered a non-serious event of clinical interest and must be reported within 24 hours to the Coordinating Center and to Merck within 2 working days.	
	Other important medical events that may not result in death, not be life threatening, or not require hospitalization may be considered a serious adverse event when, based upon appropriate medical judgment, the event may jeopardize the subject and may require medical or surgical intervention to prevent one of the outcomes listed previously (designated above by a †).	
Duration	Record the start and stop dates of the adverse event. If less than 1 day, indicate the appropriate length of time and units	
Action taken	Did the adverse event cause Merck product to be discontinued?	
Relationship to Merck Product	Did Merck product cause the adverse event? The determination of the likelihood that Merck product caused the adverse event will be provided by an investigator who is a qualified physician. The investigator's signed/dated initials on the source document or worksheet that supports the causality noted on the AE form, ensures that a medically qualified assessment of causality was done. This initialed document must be retained for the required regulatory time frame. The criteria below are intended as reference guidelines to assist the investigator in assessing the likelihood of a relationship between the test drug and the adverse event based upon the available information.	
	The following components are to be used to assess the relationship between Merck product and the AE; the greater the correlation with the components and their respective elements (in number and/or intensity), the more likely Merck product caused the adverse event (AE):	
	Exposure	Is there evidence that the subject was actually exposed to Merck product such as: reliable history, acceptable compliance assessment (pill count, diary, etc.), expected pharmacologic effect, or measurement of drug/metabolite in bodily specimen?

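### New immune-related adverse events that start after day 30 and are neither serious nor events of clinical interest need not be recorded, although late onset is expected (a cheap improvement)

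*Combined protocol and SAP*

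**What the plan says.** The 30-day limit for AEs of any kind is stated in several places. Section 7.2: "From the time of treatment allocation/randomization through 30 days following cessation of treatment, all adverse events must be reported by the investigator". Section 2.1: "each subject will be followed for 30 days for AEs monitoring". Section 5.9: "After the end of treatment, each subject will be followed for 30 days for adverse event monitoring". Section 7.1.5.3.1, on the visit at about day 30: "All AEs that occur prior to the Safety Follow-Up Visit should be recorded". That section also has AEs above Grade 1 followed until they settle or new therapy starts, so events already open at the visit are covered.

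Serious AEs have a longer clock in 7.2.3.3.2, "through 90 days following cessation of treatment, or 30 days following cessation of treatment if the subject initiates new anticancer therapy", and those related to pembrolizumab are reportable at any later time. Section 7.2.3.4 applies the same clock to ECIs, of which there are two: overdose without effects, and a combined liver-test criterion.

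On the timing of immune-related AEs, which it says may be non-serious or serious, Section 5.2.1.4 states: "These adverse events may occur shortly after the first dose or several months after the last dose of treatment".

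Two general sentences point towards wider recording. Section 7.1.2.1 speaks of recording AEs in the follow-up period, a term that 7.1.4.1 uses for the 8-weekly phase. Section 7.1.1.4.2 asks for medication taken during the trial.

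**The concern.** The protocol expects late immune-related events and keeps seeing some patients after treatment, but does not require the milder new events to be written down. In the 6.1 flow chart, the AE review row is marked at discontinuation and at the 30-day safety visit and is blank at the 8-weekly Follow Up Visits. Directed examination, blood count and chemistry are marked at those same visits. Section 5.6.1 limits medication recording after day 30 to serious AEs and ECIs, so corticosteroids given for such an event need not be recorded either.

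Toxicity is a secondary objective in both cohorts (Section 3.3), and 8.2.4 can summarise only what has been collected. If no late non-serious immune event appears in that summary, a reader cannot tell whether none occurred or nobody asked. The history also matters for patients who may be retreated in the Second Course Phase.

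**Working it through.** No sample size, power or error rate is involved, so there is no plan figure to reproduce. The check compares the collection windows and then the visit calendar.

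**Step 1. What must be recorded if a new event starts after day 30?**

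| New event | Required? | Until | Source |
|---|---|---|---|
| Serious AE, any cause except progression of the leukemia | Yes | Day 90, or day 30 if new anticancer therapy starts | 7.2.3.3.2 |
| Serious AE related to pembrolizumab | Yes | No limit | 7.2.3.3.2 |
| ECI (overdose, liver-test criterion) | Yes | Same as the first row | 7.2.3.4 |
| Event judged an important medical event | Yes, as a serious AE | As for serious AEs | 7.2.3.3, 7.2.4 |
| Any other new immune-related AE | No | – | 7.2, 6.1 |

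The last row is the gap. It is not empty in principle: Table 4 manages Grade 2 pneumonitis, colitis and nephritis with corticosteroids, and 7.2.4 assesses seriousness separately from grade, so Grade 2 is not serious in itself.

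**Step 2. Length of the interval.** From day 31 to day 90 inclusive is 90 − 31 + 1 = 60 days in which serious AEs and ECIs are collected and other new AEs are not. After day 90, only serious AEs related to pembrolizumab are required.

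**Step 3. Where the existing visits fall.** Section 7.1.5.4 gives every 8 weeks ± 14 days, and the flow chart counts from discontinuation, so visit k is on day 56k ± 14:

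- Visit 1: day 56 (42 to 70)
- Visit 2: day 112 (98 to 126)
- Visit 3: day 168 (154 to 182)

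The 90-day clock runs from cessation of treatment. If discontinuation is dated d days after the last dose, with d assumed to be 0 to 28, visit 1 falls on days 42 to 98 (70 + 28) and visit 2 on days 98 to 154 (126 + 28) after cessation. Visit 2 is always after day 90. Visit 1 is on or before day 90 unless d exceeds 20 and the end of the window is used (70 + 20 = 90). A 90-day window is therefore complete only if the first visit after day 90 asks about the time back to day 90.

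**Step 4. How late is late?** The one post-treatment onset in the protocol is a Grade 2 nephritis 5 months after the last dose (5.5.1.3, melanoma patients). That is about day 5 × 30 = 150. With d = 0 it would first be met at visit 3, beyond a 90-day window. Its seriousness is not stated, so it shows timing and not that this trial would miss such an event.

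**Step 5. Who is affected?** Only patients in the Follow-Up Phase could be helped at existing visits. After progression or new therapy there are only 12-weekly survival calls (7.1.5.4.1). The documents give neither the number of patients in follow-up nor a rate of new non-serious immune AEs after day 30, so the number missed cannot be calculated.

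**The case against.** The plan can be defended as deliberate tiering: everything to day 30, serious AEs and ECIs to day 90, serious AEs related to pembrolizumab indefinitely. The investigator can also raise a late event to serious; 7.2.4 provides for "Other important medical events that may not result in death, not be life threatening, or not require hospitalization". What remains is mostly milder and feeds only a descriptive summary. This stands, and it is why the point is a suggestion.

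Sections 7.1.2.1 and 7.1.1.4.2 can be read as already asking for the missing data, and Section 1.0 runs participation to the last protocol contact. A reader might infer a flat contradiction, or conversely that nothing is missing. The documents support neither. Section 7.1.2.1 refers to the flow chart for assessments and to 7.2 for detail, and 5.6.1 is more specific on medication than 7.1.1.4.2. The specific text governs, but the general text should be aligned.

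The existing visits are an imperfect vehicle. They include no thyroid tests, although hypothyroidism (8.3%) is the most frequent immune-mediated event in 5.5.1.3. Section 6.1 allows telemedicine for all or part of a visit. Footnote j describes a narrower group than 7.1.5.4. All of this stands and limits what the change can deliver.

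Accrual is closed, so late collection gives uneven windows. That also stands. However, Cohort 2 closed on 1/8/2020 and Section 5.9 allows 24 months of treatment, so a late enrollee could have been treated until about January 2022, and Amendment 8 (October 2020) itself changed Section 6.1. How many patients remained is unknown.

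**Conclusion.** The point holds as a low-end minor improvement. Section 7.2 and the flow chart do not require recording of a new immune-related AE that starts after day 30 and is neither serious nor an ECI, while 5.2.1.4 says such events can occur. The conclusion assumes that the specific 30-day wording overrides the general sentences.

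A reader might infer that late immune toxicity as a whole goes unrecorded. It does not: serious AEs and the liver-test ECI are reported to day 90, and serious AEs related to pembrolizumab without limit. A reader might also infer that the toxicity profile is materially understated. The documents contain nothing from which to size that, and the number is probably small. CR/CRi, the cycle 1 to 3 dose-limiting toxicity decision and the rule based on removal for toxicity (8.2.2.1) are not touched.

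**What to change.** 1. In 6.1, mark AE review at the existing 8-weekly Follow Up Visits.
2. In 7.2, 7.1.5.3.1 and 5.6.1, require Table 4 immune-related AEs of any seriousness, and corticosteroids given for them, to be recorded at those visits until progression or new anticancer therapy. If a limited window is preferred, the floor is 90 days after cessation, the existing serious AE and ECI clock, with the first visit after day 90 asking back to day 90. The longer window fits the expectation in 5.2.1.4 better.
3. Align 7.1.2.1 and 7.1.1.4.2 with this window.
4. In 8.2.4, report immune-related AEs with onset after day 30 separately, with the number of patients actually seen in follow-up as denominator.

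The cost is wording and a little data entry at visits already scheduled. Patients on telephone follow-up stay uncovered, late thyroid events would be found only if tests were added, some visits may be remote, and windows will differ between patients because accrual has ended. The report should say so.
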